DESIGN	Assessment of accuracy and precision of a novel instrument for collecting exhaled breath condensate (EBC) and analysing the levels of hydrogen peroxide.
AIMS	
(i) Assess consistency in three successive measurements at monthly intervals in individuals with COPD & healthy volunteers.(ii) Qualitative evaluation of the usability of the device and the collection protocols from participants.(iii) To collect usability feedback, in terms of how easy to use the device and to hold to breathe through the device.
OUTCOME MEASURES	
(i) Precision and accuracy of the EBC device in COPD & healthy participants. This will be assessed by comparison with the gold standard fluorometry and mass spectrometry methods.
POPULATION	COPD & Healthy subjects
DURATION	12 months

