Most previous approaches to EBC collection have prioritised the collecting of more condensate in a shorter time and this has led to the use of a lower temperature condensation surface. However, previous EBC collector designs have not considered how EBC sample composition depends on temperature and flow rate, due to widely varying absolute values and temperature dependences of the Henry's law constants for different analytes and the enthalpy of condensation. A failure to consider quantitatively the impact of collection conditions on EBC composition has led to large, reported variations between different researchers for same health condition[7-15] which has impeded progress in this field. Here we report an approach to EBC collection aimed at optimising target analyte concentration by exploiting the differential thermodynamic and kinetic parameters involved. This model-based approach is qualitatively borne out by experimental data which we have collected by blowing compressed air through Dreschel bottles of normal saline in a water bath.

The published literature largely attributes variations in EBC analyte concentration to difference in patient physiological conditions. However, Loyola *et al.* [16] demonstrated different acetone concentrations in EBC samples at difference condensation temperatures. Zamuruyev *et al.* also showed how the amount of analyte collected varies with condensation temperature.[17]

Ferric ferrocyanide (Prussian blue (PB)) modified electrodes are well-established for both H_2O_2 and oxygen sensing [18]. Karyakin *et al.* [19] demonstrated Prussian blue H_2O_2 catalysis exhibits a

significantly higher kinetic constant compared to a platinum electrochemical sensor and that PB is comparable to horseradish peroxidase. PB modified sensors were found to have good linear range between 0.1 μM to 100 μM , with sensitivity of 0.6 $\text{A M}^{-1}\text{c m}^{-2}$ and detection limit of 0.1 μM . [20]

H_2O_2 electrochemical sensor sensitivity and stability commonly involve the use of nanoparticles of PB [21], sometimes combined with polymer reagent blends [22, 23], or conducting polymers [24-26].

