The individual results of the analysis will not be made available to the participants.

The flow chart of the sample collection is shown in Figure 3 (A&B) below, C & D shows the collection device.

Participants will also be asked to fill in a short questionnaire on visit 1 related to the use of portable medical devices.

Figure 3

[figure not shown]
[figure not shown]

Figure 4 Showing 1st and 2nd Clinical Evaluation

STUDY TESTS

Apparatus during sample collection: 1 pipette, a bag of pipette tips, numbered Eppendorf vials, sterilised mouthpiece, and exhaled breath condensate (EBC) collector, 75%(v/v) aqueous ethanol solution for sterilisation of the mouthpiece and apparatus.

The following process is repeated 3 times in total to collect 3 EBC samples per participant:

1. A researcher will control device operation and sample collection.
2. The researcher switches on the device and waits until the Peltier temperature reaches 20°C, typically 1-3 minutes
3. Install the sterilised PET mouthpiece.
4. Volunteer holds the device and breathes through the PET mouthpiece normally for a maximum of 5 minutes.
5. After EBC condensation, the volunteer is to pass the device to the researcher.
6. The researcher transfers the EBC sample with pipette to vials for further analysis.
7. The EBC collector is wiped with 75% aqueous ethanol to remove remaining EBC.

Samples will be taken the Biosensor Laboratory (Bessemer 105) for analysis according to the following protocol:

Protocol for EBC analysis – electrochemical sensor and Amplex red. To take place in Bessemer 105, Biosensor Laboratory, researchers only.

All samples will be analysed. No samples will be retained.

1. Potassium phosphate monobasic, potassium phosphate dibasic, and potassium chloride salts are added to 200 µl of EBC to make pH 7.4 0.1 M phosphate buffer with 0.1 M potassium chloride.
2. 30 µl of buffered EBC is dropped onto electrochemical sensor for hydrogen peroxide analysis.
3. 48 µl of buffered EBC is withdrawn into 96-well plates with addition of 1 µl 5 U/ml horse radish peroxidase (HRP) and 1 µl 2.5mM Amplex red solution. The 96-well plates are then incubated for 30 minutes at room temperature with platform shaker before measurement with fluorometer. The excitation and absorption wavelength of the fluorometer are set to 535 and 587 nm respectively.

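### The sole outcome claims accuracy of the whole EBC device, but sensor and reference share one collected, once-buffered condensate, so only sensor accuracy can be shown

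*Protocol*

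**What the plan says.** The Design row of the Protocol's opening summary table describes a "novel instrument for collecting exhaled breath condensate (EBC) and analysing the levels of hydrogen peroxide". Its only listed outcome is "Precision and accuracy of the EBC device in COPD & healthy participants", and it continues: "This will be assessed by comparison with the gold standard fluorometry and mass spectrometry methods". Section 1.2 repeats the aim of evaluating the device's accuracy and precision in COPD.

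The term is not confined to the sensor strip. Section 4.4 says the participant holds the EBC device during collection, and Section 10 lists the device, the biosensor and the algorithm as separate items.

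The procedure is in Section 3. The apparatus list contains a "sterilised mouthpiece, and exhaled breath condensate (EBC) collector" and no second or reference collector. In the laboratory, "potassium chloride salts are added to 200 µl of EBC to make pH 7.4". Then 30 µl "of buffered EBC is dropped onto electrochemical sensor for hydrogen peroxide analysis" and 48 µl "of buffered EBC is withdrawn into 96-well plates with addition of" the Amplex Red reagents. Step 4 compares the two results by paired t tests, correlation, regression and Bland-Altman analysis. Section 7 again names fluorimetry and mass spectrometry as references; no sample or procedure for mass spectrometry is given.

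**The concern.** A method comparison can reveal only errors on which the two methods differ. Here both readings start from the same liquid, so whatever happened to the hydrogen peroxide before the split is built into the reference as well as the test.

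The collection step is not a side issue in this Protocol. Section 1.1 criticises earlier work because "previous EBC collector designs have not considered how EBC sample composition depends on temperature and flow rate", and attributes large between-researcher differences to the failure to treat collection conditions quantitatively. The study collector is offered as a response to that problem.

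At stake is the conclusion. A Bland-Altman bias near zero would be reported against an outcome labelled accuracy of the EBC device, although a biased collector would give the same result. Section 2 says the results will inform further evaluations and Section 10 plans publication, so the label would carry forward.

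**Working it through.** The Protocol has no sample size or accuracy calculation to reproduce (Section 7 says no formal calculation was made). The check is structural, followed by a numerical illustration.

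**Algebra.** Let C be the level that error-free collection and handling would deliver, and c the level in the buffered vial. Any pre-split gain or loss acts on c; write c = f·C.

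- Sensor: S = a + b·c + e1
- Reference: R = c + e2
- Difference compared in the study: S − R = a + (b − 1)·f·C + (e1 − e2)
- Error of the whole device: S − C = a + (b·f − 1)·C + e1

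If the sensor has no proportional bias (b = 1), f disappears from S − R but stays in S − C. If b ≠ 1, f only multiplies the sensor's own error (b − 1)·C. In neither case can f be separated out.

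**Inputs.**

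- From the Protocol: 15 + 15 participants, 3 visits, 3 samples per visit, so 30 × 3 × 3 = 270 pairs. Levels of 0.20 and 0.46 µM (Section 1.1) are used only to set a scale, because they are published condensate values and not known pre-collection levels. Their mean is (0.20 + 0.46)/2 = 0.33 µM.
- Assumed: f = 0.5, 1 or 1.5; collector CV 0 or 30%; assay SD 0.02 µM for each method.

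**Results.** The formulas below agree with a simulation of 300 repetitions to within about 0.001 µM.

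| Sensor | f | Mean S − R (µM) | Mean device error (µM) |
|---|---|---|---|
| Unbiased | 0.5 | 0.000 | (0.5 − 1) × 0.33 = −0.165 |
| Unbiased | 1 | 0.000 | 0.000 |
| Unbiased | 1.5 | 0.000 | (1.5 − 1) × 0.33 = +0.165 |
| 10% proportional bias | 0.5 | 0.1 × 0.5 × 0.33 = 0.0165 | (0.55 − 1) × 0.33 = −0.1485 |
| 10% proportional bias | 1 | 0.1 × 1 × 0.33 = 0.033 | (1.1 − 1) × 0.33 = +0.033 |
| 10% proportional bias | 1.5 | 0.1 × 1.5 × 0.33 = 0.0495 | (1.65 − 1) × 0.33 = +0.2145 |

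For the unbiased sensor the limits of agreement are ±1.96 × √(0.02² + 0.02²) = ±0.055 µM at every f, and a collector CV of 30% leaves them unchanged. By contrast, an additive sensor bias of 0.05 µM appears as 0.050 µM at every f. The design therefore detects sensor error and does not detect collection error.

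**Mass spectrometry.** After the two aliquots, 200 − 30 − 48 = 122 µl of buffered condensate remains. Whether mass spectrometry would use this or another portion is not stated. Section 3 sends only condensate from this device to the laboratory, so any such reading would share the collection error. Whether it would also share the buffering step cannot be told.

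**The case against.** The strongest reply is that the Protocol already shows what it means. The sentence after the outcome names analytical references for a liquid sample, Section 3 gives the purpose as analytical performance, and the comparison step speaks of the electrochemical results. On that reading only a label is loose. The description of the comparison is fair, but it is a reason to make the outcome say the same: the outcome and Section 1.2 still claim accuracy for a device that includes the collector.

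The second reply is that collection is studied. Objectives 3 and 4 cover same-day and monthly variability, and objective 5 examines standardisation using breath temperature and flow. This stands as far as it goes, and it would be wrong to say that the collector goes unexamined or is assessed by repeatability alone. But these objectives address variability, mixed with biological and sensor variation. A constant collection bias is perfectly repeatable and would pass all three.

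The third reply, that the study is preliminary, explains the absence of a sample size calculation. It does not make an outcome estimable that the data cannot inform.

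Some stronger inferences are not supported:

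- *Every pre-split influence cancels.* Effects specific to one assay, such as interference from residual ethanol after the wipe, need not, and exact cancellation requires a sensor without proportional bias.
- *The Protocol calls collection conditions the main source of error in the field.* Section 1.1 says only that neglecting them has led to large variations between researchers.
- *A collection loss would make an exacerbation look like stable disease in this study.* The published levels are already post-collection values, COPD participants must be stable at entry, and individual results are not given to participants.

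**Conclusion.** The point holds for accuracy. As designed, the comparison can support accuracy of the electrochemical sensor against Amplex Red on condensate from this collector. It cannot support accuracy of the whole device, and no later analysis of the same data can recover a bias that both readings share.

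The size of any hidden error is unknown, because the documents give no recovery figure for the collector. The 0.165 µM above follows from assumed factors of 0.5 and 1.5 and shows only that a large collection error can coexist with zero observed bias.

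The conclusion rests on two readings of the text: that the device includes the collector, as the Design row and Sections 4.4 and 10 indicate, and that no independent reference for the collection step exists in the participant study, since none is described. A reader might infer that the sensor comparison itself is flawed or that precision is equally untested. Neither follows: a split-sample comparison is suitable for the sensor, and the replicates do bear on precision.

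**What to change.** Restate the outcome in the summary table, and the matching aim in Section 1.2, as *accuracy of the electrochemical sensor against the reference assay in EBC collected with the device*. State beside it that the collector is assessed through volume collected, same-day and monthly variability, and the temperature and flow standardisation method (objectives 1 and 3 to 5). Limit the planned conclusion and publication wording in the same way. If mass spectrometry is kept as a reference, say which portion of the condensate it reads.

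This is a change of wording; its cost is a narrower claim.

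If a device-level accuracy claim is to be kept, it needs a separate reference for the collection step. One option is bench recovery of known hydrogen peroxide concentrations passed through the clinical collector, including after the ethanol wipe, reported next to the clinical agreement. It could build on the saline-bottle set-up in Section 1.1, whose data are described there as only qualitative support, and would need no participants. It is optional if the outcome is narrowed.

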1.2 Study Rationale

Following a successful pilot study and a clinical assessment in healthy volunteers (1st Clinical Evaluation) we now want to evaluate the accuracy and precision of the EBC device in patients with COPD (2nd Clinical Evaluation). We want to evaluate the reproducibility of 3 measurements a month apart in real breath samples in the same manner as the previous clinical evaluation with healthy volunteers. This will take place at the Clinical Research Facility (CRF) at the Royal Brompton Hospital. Real biological specimens are complex and there is the potential for losses of precision and accuracy. This can only be evaluated by comparison with established methodology. Secondly, whilst many reports can correctly classify COPD patients, there are substantial variations in absolute levels between researchers. We have shown with artificial samples that correcting for variations in heat and mass transport can substantially reduce these variations. Collecting replicate samples from patients with COPD will allow us to evaluate this approach in this patient group.

2. STUDY OBJECTIVES 2

The questions to answer in clinical evaluation:

1. Volume collectable in 3-5 minutes,
2. Concentration of hydrogen peroxide in COPD and healthy subjects,
3. Variability between 3 samples collected in 1 day,
4. Variability between 3 tests collected in 1st month, 2nd month and 3rd month,
5. Usefulness of standardisation method, data including breath temperature entering and leaving the device as well as breath flow rate would be collected in-situ (sensors already on device, no naked wires),
6. Usability feedback, in terms of how easy to use, to hold and to breathe through the device

The outcomes of this study will inform the design of further clinical evaluations.

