3. STUDY DESIGN

Venue: This will be performed in the Clinical Respiratory Facility located at the Royal Brompton Hospital.

We aim to recruit 15 patients with COPD and 15 healthy volunteers from our database of volunteers at the royal Brompton Hospital. Our purpose with this study is to evaluate the analytical performance of the device and the data processing and consistency of measurements over a 3-month period.

Three successive measurements will be made at monthly intervals in each patient with COPD and with each healthy volunteer requiring them to visit the Hospital on three occasions. The first visit also includes screening which will take up to 1 hour.

Firstly, each potential participant will be sent a participant information sheet.

If they decide that they wish to take part in the research study, they will be asked to come to the Clinical Research Facility (CRF) at the Royal Brompton Hospital, for screening where the

research team will further explain the study to the participant. A hard copy of the participant information sheet will be provided at the appointment and participants will be encouraged to ask questions. Participants will then be presented with a consent form which they will be asked to sign before any procedures are made.

As part of screening, they will have a baseline screening questionnaire including a check of medications they are currently taking.

If the participant satisfies the screening criteria, they can then enter the study. After the consent form has been signed, participants will perform spirometry measurements prior to the following the breath collection procedures. These procedures will be performed on each study visit.

An exclusion questionnaire will be presented at the appointment.

Sample collection protocol

The handheld breath collection apparatus will be switched on by the researcher and allowed to achieve the correct temperature (1-2 minutes). A sterilised disposable plastic mouthpiece will be fitted. The participant will be asked to hold the breath collection device and breathe normally into the plastic mouthpiece for up to 5 minutes (Figure 3).

The researcher will take the instrument and remove the condensed breath sample, place it in a numbered vial and remove it for analysis in the laboratory. Ideally, three samples per participant will be collected, but the participant may withdraw consent at any point.

It will not be possible to identify the participant from the sample labelling.

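### The only stated outcome assesses precision by comparison with reference assays, which cannot show the within-day and month-to-month consistency the study sets out to measure

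*Protocol*

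**What the plan says.** The Design row of the Protocol synopsis describes the study as "Assessment of accuracy and precision of a novel instrument for collecting exhaled breath condensate (EBC) and analysing the levels of hydrogen peroxide". The Outcome measures row has a single entry, precision and accuracy of the device in both groups, followed by: "This will be assessed by comparison with the gold standard fluorometry and mass spectrometry methods".

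The purpose is put differently elsewhere:

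- Synopsis, aim (i): "Assess consistency in three successive measurements at monthly intervals in individuals with COPD" (and in healthy volunteers).
- Section 1.2: "We want to evaluate the reproducibility of 3 measurements a month apart in real breath samples".
- Section 2, objective 3: "Variability between 3 samples collected in 1 day".
- Section 2, objective 4: "Variability between 3 tests collected in 1st month, 2nd month and 3rd month".
- Section 3 includes in the purpose "consistency of measurements over a 3-month period".

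The laboratory steps in Section 3 buffer each condensate sample, then take 30 µl for the sensor and 48 µl for Amplex Red. Step 4 compares the two by paired t tests, correlation, regression and Bland-Altman analysis. Section 7 gives consistency as the reason for having no sample size calculation and says Bland-Altman plots will be used, without saying what they compare. It then says performance will be judged against the reference methods.

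**The concern.** The outcome statement puts precision and accuracy under one method, a comparison between assays. That comparison shows bias and the random error that the two assays do not share. It does not show how far a person's readings move between samples on one day or between months.

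It also starts after the condensate has been collected, although the instrument is described as one that collects as well as analyses. Collection variability reaches both assays alike and so drops out of their difference.

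The study could therefore report its one stated outcome in full, and favourably, without answering aim (i) or objectives 3 and 4. Section 2 adds: "The outcomes of this study will inform the design of further clinical evaluations". Those evaluations will need the within-person SD. As context only, Section 1.1 gives typical levels of 0.46 µM in COPD and 0.6 µM in exacerbation and calls the range limited. That 0.14 µM gap is between literature group levels. It is neither a within-person change nor a study criterion.

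**Working it through.** The Protocol gives no precision or sample size figure to reproduce. The check has two parts.

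**1. What the comparison can detect**

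Let T be the true level in a condensate sample, made up of person, month and within-day (collection) components. The sensor reads kT + e₁ and the reference reads T + e₂, where k is the sensor's slope relative to the reference. The difference is (k − 1)T + e₁ − e₂. At k = 1 with error independent of level, T vanishes.

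The Protocol gives no SDs, so these are assumed: mean 0.46 µM (the COPD level in Section 1.1), between-person SD 0.15, within-day SD 0.07, and error SD 0.05 in each assay. The between-month SD, s, is raised from 0.02 to 0.20 µM.

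- Half-width of limits of agreement: 1.96 × √[(1 − k)²(0.15² + 0.07² + s²) + 2 × 0.05²]
- Month-apart repeatability coefficient of the sensor: 1.96 × √2 × √[k²(0.07² + s²) + 0.05²]

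| Slope k | Limits half-width, s = 0.02 → 0.20 | Repeatability coefficient, s = 0.02 → 0.20 |
|---|---|---|
| 1.0 | 0.139 → 0.139 (no change) | 0.245 → 0.603 (×2.46) |
| 0.8 | 0.153 → 0.172 (×1.12) | 0.213 → 0.490 (×2.30) |
| 1.2 | 0.153 → 0.172 (×1.12) | 0.279 → 0.718 (×2.57) |

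At k = 1, for example, the limits are 1.96 × √0.005 = 0.139 whatever s is. The repeatability coefficient goes from 2.772 × √0.0078 = 0.245 to 2.772 × √0.0474 = 0.603.

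If assay error is instead 10% of the level, the limits widen by 8% at k = 1 (0.136 to 0.146), 20% at k = 0.8 (0.139 to 0.167) and 17% at k = 1.2 (0.163 to 0.191). The repeatability coefficient rises 2.49-fold in each case.

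A separate simulation used other assumed values: 15 participants × 3 visits × 3 samples, 4,000 runs, between-person SD 0.10, sensor error 0.05, reference error 0.03. Month and within-day SD were both set to 0, 0.05, 0.10 or 0.20 µM. The limits stayed at ±0.114 µM in all four cases. The estimated within-day SD, which includes sensor error, went from 0.050 to 0.206 µM. The estimated month SD went from about 0.006 to 0.197 µM.

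**2. What the planned replicates can estimate**

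This takes three samples at each visit, inferred from objective 3 and from Section 3 repeating the procedures at every visit. Per group with complete data there are 15 × 3 × 3 = 135 readings. The 95% CI factor for an SD on a given df is √(df/χ²).

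| Quantity | df | CI factor |
|---|---|---|
| Within-day SD, 3 samples per visit | 15 × 3 × 2 = 90 | 0.87 to 1.17 |
| Within-day SD, 2 samples per visit | 15 × 3 × 1 = 45 | 0.83 to 1.26 |
| SD of visit means | 15 × 2 = 30 | 0.80 to 1.34 |

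The two-sample row is shown because Section 3 presents three samples as the ideal. For the between-month SD alone, a generalised CI gives factors of 0.71 to 1.43 if it equals the within-day SD. If it is half the within-day SD, the factors are about 0.15 to 1.69; the lower bound moved between 0.12 and 0.15 across runs.

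**The case against.** The strongest reply is that two different things are meant. Section 1.2 speaks of precision and accuracy being lost in complex biological specimens and says only comparison with established methods can evaluate this. That is analytical performance, and the spread of sensor-minus-reference differences does carry it. Consistency is then a separate question, already listed in Section 2, and the Bland-Altman sentence in Section 7 could cover repeats. On this reading a report without repeatability would fail the objectives, whatever the outcome row says. That row is in any case not exhaustive: usability and collectable volume are absent from it too. Model detail belongs in a SAP.

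Parts of this stand. The comparison does inform on analytical error, though it cannot separate the sensor's error from the reference's. Month-to-month variability is not device precision alone. The choice of model can be left to a SAP. Three samples per visit is an inference, if a well-supported one. The illustration rests on assumed SDs and a chosen tenfold rise; 0.20 µM is 43% of the 0.46 µM mean, and no healthy-level case is shown.

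The conflict remains. Consistency is the main purpose, not a side question, and the one outcome statement sends precision elsewhere. The instrument includes the collection step, which the comparison cannot see. Step 4 of the laboratory protocol ties Bland-Altman to Amplex Red, and nothing in the Protocol names an analysis of repeats. A SAP should not have to override an outcome definition.

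**Conclusion.** The concern holds and should be fixed. The assessment rule in the synopsis does not estimate what aim (i) and objectives 3 and 4 ask for. Where month-to-month variation is made ten times larger, the limits of agreement change by between nothing and 20%, while the month-apart repeatability coefficient more than doubles. The sizes depend on the assumed SDs. The cancellation does not, provided both assays read the same sample; it is exact only with equal slopes and error that does not depend on level. This is shown for Amplex Red. The Protocol does not say which sample mass spectrometry reads.

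The data already planned can answer the question: well for within-day variability, and less precisely for the between-month component if that is small.

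**What to change.** In the synopsis, split the outcome in two:

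- **Agreement (accuracy):** sensor against the reference methods by Bland-Altman analysis, allowing for repeated measurements per participant.
- **Repeatability:** from the replicate sensor readings, separately for COPD and healthy participants, a variance-components analysis (participant, visit, sample). Report the within-day and between-month SD or CV, and the same-day and month-apart repeatability coefficients, with 95% CIs.

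Label the month-apart figure as total within-person variability (device, collection and true change), not as device precision alone. The paired Amplex Red readings, with a slope allowed between assays, can help separate assay error from change in the sample. In Section 7, repeat the split and say what the Bland-Altman plots compare. Model detail may go in the SAP.

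The cost is one sentence in the synopsis, one or two in Section 7 and modest extra analysis, with no new data. Two limits should be accepted. With 15 per group, a small between-month component will be imprecise. The separation of assay error is also rough: in 5,000 simulated groups, an assumed sensor error SD of 0.05 µM was estimated between about 0.035 and 0.063 µM, and was biased to about 0.041 µM when a true slope of 0.8 was ignored.
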